Whilst a patient is being considered for an intra-patient dose escalation, they should continue treatment at their allotted dose level. In the event of an intra-patient dose escalation, such patients will not be evaluable for DLT at the escalated dose.

After each patient has completed the DLT assessment period during the dose escalation phase of the study, the SRC will evaluate all available toxicity information (including AEs and laboratory abnormalities that are not DLTs), as well as available PK and PD information for the first cycle for all evaluable patients (data from Cycle 2 and beyond will also be evaluated if available). Additional CRF data may be included in the SRC review including vital signs, clinical chemistry/haematology, ECG results, PK and PD data, ad hoc safety reports, AEs from previous cohorts and optional expansions and any other emerging data. If appropriate, quantitative dose/exposure-response models will be used to describe the relationship for such data of interest to decide the next dose and/or schedule.

There is no limit to the number of intra-patient dose escalations that a patient can undergo.

Intermediate dose levels, dosing intervals and/or frequency, and/or schedules may be evaluated prior to declaring the RP2D, which will be guided by the evolving safety, preliminary efficacy, PK and PD data.

For decisions on dose escalation (Part A), an evaluable patient is defined as a patient that has received AZD7648 and either:

• Has completed minimum safety evaluation requirements and has received at least 75% of the total amount of planned dose of AZD7648 (and PLD for Combination Module 1) during Cycle 1

or

• Has experienced a DLT during Cycle 0 or Cycle 1.

Triggers for Additional Modules

Combination modules, eg, Combination Module 1 (combination of AZD7648 + PLD) will start after PK data from monotherapy dose escalation has confirmed an understanding of the metabolic profile of AZD7648 and the dose selected as the starting dose for the combinations is safe and tolerated. Triggers that will initiate the start of additional combination modules may include (but are not limited to):

- PK dose proportional. PK exposure vs. dose is well understood.

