6.1.3 Definition of dose-limiting toxicity

DLTs will be evaluated during Cycle 0 and Cycle 1 of treatment. Toxicity will be graded according to the National Cancer Institute CTCAE v5.0.

A DLT is defined as an AE that occurs from the first dose of study treatment up to and including Cycle 1, Day 28 (the DLT assessment period) that is assessed as unrelated to the disease, intercurrent illness, or concomitant medications and that, despite optimal therapeutic interventions, meets any of the following criteria:

Haematological Toxicities:

- Grade 4 neutropenia lasting > 4 days.
- Grade 4 thrombocytopenia.
- Grade \geq 3 neutropenia (ANC < 1000 cells/mm³ [< 1 x 10⁹/L]) of any duration accompanied by fever \geq 38.5°C and/or systemic infection.
- Grade \geq 3 thrombocytopenia (< 50,000/mm³ [< 50 x 10⁹/L]) with bleeding.

Non-haematological Toxicity CTCAE Grade ≥3 Including:

- Confirmed laboratory abnormalities greater than 72 hours of duration.
- Nausea or vomiting for more than 3 consecutive days despite administration of maximal anti-emetic therapy.
- Diarrhoea for more than 3 consecutive days despite administration of maximal anti-diarrhoeal therapy.
- QTc prolongation > 500 milliseconds or QTcF prolongation from baseline by 60 milliseconds confirmed on at least 2 separate ECGs.
- Any other toxicity that is greater than that at baseline AND is clinically significant and/or unacceptable, and does not respond to optimal therapeutic intervention within 72 hours AND is judged to be a DLT by the SRC.
- Any treatment-related event, including significant dose reductions, omissions or delays, judged to be a DLT by the SRC. Examples may include CTCAE Grade 2 toxicities that are clinically significant and/or unacceptable according to the Investigator, toxicities that result in an inability to administer at least 75% of study treatment during Cycle 1 or delay the administration of study treatment in the subsequent cycle by ≥ 7 consecutive days.

DLT Will not Include the Following:

- Transient isolated laboratory abnormalities which are not considered clinically significant and resolve to baseline within 72 hours without any intervention.
- Alopecia.
- Toxicity unrelated to treatment eg, related to the underlying disease or disease-related process under investigation.
- Grade 4 vomiting and diarrhoea lasting < 72 hours in the absence of maximal medical therapy.

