- Grade 3 nausea, vomiting or diarrhoea that lasts < 48 hours and resolves to Grade ≤ 1 either spontaneously or with maximal medical therapy.
- Grade 3 fatigue < 5 days.
- Grade 3 hypertension in the absence of maximal medical therapy.
- Grade 3 electrolyte abnormalities that resolve to Grade ≤ 1 within 48 hours spontaneously or with conventional medical intervention and is not clinically complicated.
- Grade 3 rash that resolves to Grade ≤ 1 within 3 weeks.
- Grade 3 or Grade 4 elevation in serum amylase and/or lipase that are not associated with clinical or radiographic evidence of pancreatitis.

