6.6 Dose modification

Details of dose escalation can be found in Section 6.1.2.

Study treatment will be repeated in 28-day cycles. The dosing criteria for Day 1 of a new cycle of study treatment (blood tests should be reviewed prior to dosing) and continuation of treatment are:

- ANC $\geq 1500 \text{ cells/mm}^3 (\geq 1.5 \text{ x } 10^9/\text{L})$
- platelets \geq 75,000/mm³ (\geq 75 x 10⁹/L)

If a patient experiences a clinically significant and/or unacceptable toxicity (including a DLT) study treatment will be interrupted (and appropriate treatment administered) for a maximum of 28 days until resolution of the toxicities to the patient's baseline or until improvement (CTCAE Grade ≤ 2) (Table 6). Clinically significant abnormal laboratory values must be repeated at regular intervals until resolved to the patient's baseline or until improvement (CTCAE Grade ≤ 2). If the patient is showing clinical benefit and the toxicity resolves to the patient's baseline or until improvement (CTCAE Grade ≤ 2). If the patient (CTCAE Grade ≤ 2), treatment can be restarted; guidelines are provided below for dose modifications (Table 7).

If the toxicity does not resolve to the patient's baseline or to CTCAE Grade ≤ 2 within 28 days of onset, treatment with AZD7648 must be discontinued.

Event (CTCAE V5.0)	Action
Grade 1 to 2 toxicity (all events)	Investigator judgement to continue treatment or interrupt dose (maximum 28 days), except for Day 1 of a new cycle of study treatment, as described above. Initiate optimal supportive care and causality investigation. Consider resuming at the same dose level when toxicity has resolved or is resolving with prophylactic treatment (if appropriate). If toxicity recurs on rechallenge and does not resolve in < 7 days despite optimal supportive care, consider a dose reduction.
Grade 3 to 4 toxicity (1 st event)	Interrupt study treatment, initiate optimal supportive care and causality investigation. Maximum treatment interruption is 28 days. When toxicity has resolved or is resolving with prophylactic treatment (Grade ≤ 2 or returns to baseline), consider re-starting AZD7648 with 1 dose level reduction and prophylactic treatment (if appropriate).

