2.2 Analysis sets

All patients who receive any amount of study treatment will be included in the safety analysis. For the safety summaries, patients who received study treatment will be presented by module, by part, by cohort and planned starting dose level and dose frequency. Actual dose level and frequency received by patients within each planned cohort will be summarised separately.

For all efficacy analyses, and for baseline and demography summaries, patients are classified according to the module, part, cohorts and the dose they were randomised/assigned to (i.e. the planned treatment/dose level/dose schedule)

The plasma concentrations of AZD7648 and PLD for each scheduled time point will be summarised by module, cohort (dose regimen) and Cycle/PK day (single dose or multiple dose) based on the pharmacokinetics set. The dosing regimen used throughout the PK outputs includes both the dose level and dose frequency of the analyte and should be the planned (protocol scheduled) dosing regimen, although ad hoc summary tables and figures may be requested to include data from patients from a different cohort who were either mis-dosed or where the dose level was the same but the frequency was different (would apply to single dose PK data only).

Details of the analysis sets are presented in [Table 2](#).

Table 2: Analysis sets

Analysis Set	Definition
Enrolled	All patients who signed the informed consent.
Safety set	All patients who received at least 1 dose of any study treatment
Pharmacokinetics (PK) set	All patients who received at least 1 dose of any study treatment with at least one reportable post first dose

	concentration without any protocol deviations that might affect PK.
Evaluable for objective response set	All patients who had a measurable baseline disease ^[a] by RECIST 1.1 assessment and received at least one dose of any study treatment.
Evaluable for efficacy set	All patients who received at least 1 dose of any study treatment and have a baseline tumour assessment according to RECIST 1.1.
DLT evaluable set ^[b]	All patients who received at least 1 dose of any study treatment and either experienced DLT during the cycle 0 or 1, or who completed minimum safety evaluation requirements and has received at least 75% of the total amount of planned dose of AZD 7648 (and PLD for combination Module 1). In the event of an intra-patient dose escalation, such patients will not be evaluable for DLT at the escalated dose.

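### A patient who loses over a quarter of the Cycle 1 dose to an excluded toxicity can leave the DLT-evaluable set, so the reported DLT rate may read low

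*Protocol*

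**What the plan says.** Protocol 6.1.3 has two lists. The first sets out what can be a DLT. Its last item covers any treatment-related event that the SRC judges to be one, and its examples include "toxicities that result in an inability to administer at least 75% of study treatment during Cycle 1". The second sets out what DLTs will not include. Three entries matter here:

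- "Grade 3 nausea, vomiting or diarrhoea that lasts < 48 hours", provided it resolves to Grade 1 or less;
- "Grade 4 vomiting and diarrhoea lasting < 72 hours in the absence of maximal medical therapy";
- "Grade 3 rash that resolves to Grade ≤ 1 within 3 weeks".

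None of the three has an exception for lost dose, and no sentence ranks the two lists.

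For a first Grade 3 to 4 toxicity, Protocol 6.6 Table 6 says: "Interrupt study treatment, initiate optimal supportive care and causality investigation". It then asks the investigator to consider restarting one dose level lower.

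Under Protocol 6.1.2 a patient counts for escalation if they had a DLT in Cycle 0 or 1, or if the patient "Has completed minimum safety evaluation requirements and has received at least 75% of the total amount of planned dose of AZD7648". Protocol 9.3 and SAP 2.2 define the DLT evaluable set in the same way (SAP: "completed minimum safety evaluation requirements and has received at least 75% of the total amount of planned dose of AZD 7648"). SAP 3.2.1.3 repeats the rule, adds that patients who withdraw within the first 28 days for a reason other than a DLT are not evaluable, and takes both the DLTs and the evaluable list from SRC decisions. SAP Table 3 reports DLTs on this set.

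**The concern.** The evaluability rule is meant to stop under-dosed patients from diluting the DLT rate. It works if low dosing is unrelated to toxicity, or if toxicity that causes low dosing is called a DLT. The exclusion list leaves a gap between the two. A patient can lose more than 25% of the Cycle 1 dose because of a treatment-related Grade 3 or 4 event, have that event fall under an exclusion, and so be neither a DLT nor evaluable. The exclusion is then informative.

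DLTs are among the primary endpoints. A rate that drops patients because of toxicity is lower than one that counts them, and no planned output shows how many were dropped for this reason.

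**Working it through.** There is no stated figure to reproduce, because the plan attaches no number to this rule. The check has three parts.

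**1. Can an excluded event take a patient below 75%?**

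Inputs: 28-day cycle (Protocol Table 1); continuous schedule and a schedule of 7 dosing days per cycle (SAP 3.2.1.1); later dose steps of at most 50% (Protocol Table 4). Planned dose is taken as the assigned dose without modification, the convention that SAP 3.2.1.2 uses for intended dose. Actual doses are redacted, so step sizes are assumptions.

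- 7-day schedule: 1 missed day leaves 6/7 = 86%; 2 leave 5/7 = 71%; 3 leave 4/7 = 57%. Two missed dosing days are enough. An event on the last dosing day or in the off period is not.
- Continuous, no reduction: 2 missed days leave 26/28 = 93%; 7 leave 21/28 = 75% (still evaluable); 8 leave 20/28 = 71%.
- Continuous, *d* full-dose days, 2 missed days, then a fraction *f* of the dose: share = (*d* + (26 − *d*)*f*)/28.
  - 50% step, *f* = 2/3: *d* = 10 gives 20.67/28 = 73.8%; *d* = 11 gives 21/28 = 75.0%. Below 75% up to *d* = 10.
  - Doubling step, *f* = 1/2: *d* = 15 gives 20.5/28 = 73.2%; *d* = 16 gives 75.0%. Below 75% up to *d* = 15.
  - 25% step (assumed), *f* = 0.8: *d* = 0 gives 20.8/28 = 74.3%; *d* = 1 gives 75.0%. Below 75% only at *d* = 0.

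The overlap is therefore realistic on the 7-day schedule. On continuous dosing it needs a reduction, a hold of 8 or more days, or discontinuation, which Protocol 6.6 requires if a reduction is needed at the first dose level. If planned dose meant the dose after reduction, the reduction route would close and the two-day case would stay at 93%.

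**2. What happens to the DLT proportion?**

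| Cohort | Called a DLT | Kept as non-DLT | Dropped |
|---|---|---|---|
| 3 patients, no other DLT | 1/3 = 33% | 0/3 | 0/2 |
| 6 patients, one other DLT | 2/6 = 33% | 1/6 = 17% | 1/5 = 20% |

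In general, let *p* be the rate of clear DLTs and *q* the rate of these events. Counting gives *p* + *q*; dropping gives *p*/(1 − *q*). Since (*p* + *q*)(1 − *q*) = *p* + *q*(1 − *p* − *q*), dropping always gives the lower figure when *p* + *q* < 1. With assumed *p* = 20% and *q* = 5% to 15%, counting gives 25% to 35% and dropping gives 21.1% to 23.5%. The bias is downward relative to counting the events as DLTs; relative to keeping them as non-DLTs, dropping raises the rate slightly.

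**3. What did this mean for escalation?**

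Protocol 6.1.2 needs 2 evaluable patients of 3 for an escalation meeting, and allows escalation without the model while no DLT has been seen at any dose. So 0/2 met the formal rule, while 1/3 would have brought the model into use. With assumed *p* = 20% and *q* = 10%, the chance that three patients show no DLT with at least two evaluable is 0.7³ + 3 × 0.7² × 0.1 = 49.0% if such patients are dropped, against 0.7³ = 34.3% if they are counted.

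**The case against.** The strongest reply is that the SRC settles this. The 75% item does not itself classify anyone: it gives examples of what the SRC may judge to be a DLT, and Protocol 6.1.4 lists determining DLTs among the SRC's powers. The two lists can also be reconciled by reading the exclusion as covering the brief event and the SRC item as covering the lost dosing. That stands. A reader might infer that the protocol gives two contradictory verdicts on the same patient; the text does not go that far. What remains is that nothing says whether the exclusion limits the SRC's discretion, and that a patient below 75% drops out whenever the SRC does not call a DLT.

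A second reply is that the toxicity stays visible. Protocol 6.1.2 has the SRC review toxicities that are not DLTs, and it can hold, expand or de-escalate. The SAP summarises Grade 3 or higher AEs, AEs leading to discontinuation, dose intensity, and interruptions and reductions in the first 28 days. So the inference that toxicity is hidden, or that escalation was unsafe, is not supported. But none of these outputs identifies who left the DLT denominator because of toxicity.

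Third, the overlap is narrow. Table 6 only asks the investigator to consider a reduction, and an elective reduction is not plainly an inability to dose. Restart is allowed at Grade 2 or less, so the three-week rash limit does not imply a three-week hold. The doubling case belongs mainly to early single-patient cohorts, where a related Grade 2 or higher event already ends single-patient titration. All of this stands.

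Finally, a reader might see the Grade 4 exclusion (under 72 hours) as inconsistent with the narrower Grade 3 one (under 48 hours). The lead-in to 6.1.3 requires the toxicity to occur despite optimal treatment, which partly explains a Grade 4 exclusion limited to cases without maximal therapy. On less than maximal therapy, 60 hours of Grade 3 diarrhoea misses the named criterion too and can only reach the SRC by discretion. The mismatch is a drafting matter.

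**Conclusion.** The point holds as a limited reporting issue, and the change is optional. Followed exactly, the evaluability rule can remove a patient from the DLT rate because of treatment toxicity, through an excluded event that the SRC does not call a DLT. One such patient changes 1/3 to 0/2, or 2/6 to 1/5. The cohort proportions and the 7-day result (71% after two missed days) need only the stated rules and the unmodified-dose convention. The continuous-dosing results with a reduction also rest on assumed step sizes, and the rate and probability illustrations on assumed event rates. No case is documented. Since SAP Version 4.0 records that development was halted and the outputs reduced to focus mainly on safety, what can still change is how DLTs are reported.

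**What to change.** In SAP 3.2.1.3, report by cohort the patients who were not DLT-evaluable because treatment-related toxicity took them below 75% of the Cycle 1 dose or led them to withdraw, with the event and grade. Beside the SRC-approved DLT count, give a supplementary count, clearly labelled as an upper bound, that includes these patients as DLTs. SRC decisions stay as they are. If the number is zero, the table supports the reported rate.

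The cost is a line or two in the DLT table; dosing records and AE dates and grades are already collected. The small downside is that the supplementary figure may look less favourable and may include cases that the SRC considered and rejected, hence the label.

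If 6.1.3 is amended or reused, add one sentence: the exclusions do not apply when the event prevents 75% of Cycle 1 dosing or delays the next cycle by 7 days or more, in which case the SRC decides. Aligning the Grade 4 vomiting and diarrhoea limit with the Grade 3 limit is a secondary tidy-up.

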6.1.3.1 Definition of Maximum Tolerated Dose and Recommended Phase II Dose

The MTD is defined as the highest dose at which the predicted probability of a DLT is less than 25% (for monotherapy) or 30% (for combinations). At least 6 evaluable patients are required to determine the MTD (refer to Section 6.1.2 for a detailed description of the Bayesian adaptive design).

The RP2D will take into account the MTD (or alternative doses/schedules in the absence of MTD), MFD, PK, biological/clinical activity (PD data), as well as data beyond Cycle 1 during dose escalations.

6.1.3.2 Definition of Maximum Feasible Dose

A dose and schedule will be considered to be the MFD and dose escalation will stop if:

• There is evidence of saturation of absorption from emerging PK data that limits the exposure

and/or

• An MFD has been reached, based on a maximum number of tablets per dose or day, or the maximum dose permitted based on CMC quality specifications (currently set against a maximum dose of CCI mg CCI = CCI mg/day), whichever is the lower dose.

6.1.4 Safety review committee

The SRC Remit document for this study will define the exact membership and who will be present for decisions to be made.

The SRC will guide all dose escalation and cohort expansion decisions in this study. The dose or schedule for subsequent cohorts or a decision to stop recruitment will be agreed by the SRC after review of the data from each cohort. When there are other patients that are ongoing at the time a review is planned, the SRC should defer their decision until these further patients become evaluable. The data which will be reviewed at a dose decision meeting includes (but is not limited to):

- All available safety information and laboratory abnormalities (including clinically significant AEs and laboratory safety variables).
- Data on exposure eg, any dose interruptions or reductions.
- All available PK (mandatory Cycle 0 and Cycle 1 PK data in single patient cohorts up to and including ^{CCI} for Cohorts 1 to 4) and PD data.
- The dose recommended from the Bayesian model.

The SRC can decide at each meeting to:

- Determine DLTs
- Change the schedule of drug administration
- Stagger enrolment into a cohort based on toxicity in the sentinel patient
- Stop enrolment into a cohort
- Recommend a temporary halt on further dosing of patients to allow further evaluation of patients
- Stop further dosing of all patients in the study

- Escalate the dose
- Expand the cohort to a maximum of 6 evaluable patients
- De-escalate the dose
- Initiate the combination modules of AZD7648
- Stop the dose escalation
- Adjust the dosing frequency, schedule or sequence of AZD7648, with or without a concurrent change in dose
- Adjust the dosing frequency, schedule or sequence of the combination agent, with or without a concurrent change in dose
- Initiate optional expansion cohorts (PD and/or efficacy expansion and/or food effect cohorts)
- Declare the MTD, MFD, and/or RP2D for the Core Module or combination modules
- Initiate Part B cohort expansions
- Stop Part B of a study module
- Permit a patient to dose escalation (intra-patient dose escalation).

Investigators will be provided with written confirmation of the next dose level based upon the SRC decision. Regulators/ethics bodies will be formally notified, as required by local regulation, of an SRC recommendation to temporarily halt or prematurely stop the study.

6.2 **Preparation/handling/storage/accountability**

The Investigator or designee must confirm appropriate temperature conditions have been maintained during transit for all study treatment received and any discrepancies are reported and resolved before use of the study treatment.

Only patients enrolled in the study may receive study treatment and only authorised site staff may supply or administer study treatment. All study treatments must be stored in a secure, environmentally controlled, and monitored (manual or automated) area in accordance with the labelled storage conditions with access limited to the Investigator and authorised site staff.

The Investigator, institution, or the head of the medical institution (where applicable) is responsible for study treatment accountability, reconciliation, and record maintenance (ie, receipt, reconciliation, and final disposition records).

Further guidance and information for the final disposition of unused study treatment are provided in the Pharmacy Manual.

6.3 Measures to minimise bias: randomisation and blinding

This is an open-label study; no blinding is required.

In case of parallel recruitment to Part A and Part B (in the combination modules), a suitable patient allocation system will be implemented to manage any potential bias.

If an unscheduled assessment is performed, and the patient has not progressed, every attempt should be made to perform the subsequent assessments at their scheduled visits. This schedule is to be followed to minimise any unintentional bias caused by some patients being assessed at a different frequency than other patients.

